2 LIST OF ABBREVIATIONS

[figure not shown]
AE	Adverse Events
AED	Anti-Epileptic Drug
ALK	Alkaline Phosphatase
ATRX	Alpha-Thalassemia/mental Retardation syndrome X-linked gene
BID	Twice a Day (from Latin bis in die)
[Ca ²⁺] _i	Intracellular calcium
CAP	College of American Pathologists
CBC	Complete Blood Count
CBZ	Carbamazepine
CICR	Calcium-induced calcium release
CLIA	Clinical Laboratory Improvement Act
CNS	Central Nervous System
COLA	Commission on Office Laboratory Accreditation
CrCL	Creatinine Clearance
CPC	Cancer Protocol Committee
CRF	Case Report Form (eCRF is for electronic CRF)
CTCAE	Common Terminology Criteria for Adverse Events
CYP	Cytochromes P450
DCI	Duke Cancer Institute
DNA	Deoxyribonucleic Acid
DSMB	Data Safety Monitoring Board
DUHS	Duke University Health Systems
DUMC	Duke University Medical Center
EIAED	Enzyme Inducing AED
EMA	European Medicines Agency
ESRD	End Stage Renal Disease
FDA	US Food and Drug Administration
GABA	Gamma-Aminobutyric Acid
GCP	Good Clinical Practice
GTC	General tonic-clonic
GTR	Gross Total Resection
HGG	High Grade Glioma
HRPP	Human Research Protection Program
HRQOL	Healthcare related quality of life
ICH	International Conference on Harmonization
IEC	Institutional Ethics Committee
ILAE	International League Against Epilepsy
IP3	Inositol 1,4,5-triphosphate
IRB	Institutional Review Board
IT	Information Technology
IV	Intravenous
KPS	Karnofsky Performance Score
LCM	Lacosamide
LGG	Low Grade Glioma
LEV	Levetiracetam
LTG	Lamotrigine
MGMT	O-6 Methylguanine-DNA Methyl Transferase
MSR	Maximum Safe Resection (gross-total, sub-total, biopsy)
NS-CRU	Neurosurgery-Clinical Research Unit
OARC	Office of Audit, Risk and Compliance
PBT	Phenobarbital

PHT	Phenytoin
PI	Primary InvestigatorQAP Quality Assurance Program
QID	Four times each Day (from Latin quater in die)
QOL	Quality of Life
QOLIE	QOL in Epilepsy
RCA	Research Compliance Assurance
REDCap	Research Electronic Data Capture™
RIO	Research Integrity Office
RDSP	Research Data Security Plan
RyR	Ryanodine
SAE	Serious Adverse Effect
SGOT	Serum Glutamic Oxaloacetic Transaminase
SGPT	Serum Glutamic Pyruvic Transaminase
SOC	Standard of Care
SOCOMM	Safety Oversight Committee
SOPs	Standing Operating Procedures
STR	Sub-total resection
POS	Partial Onset Seizures
ULN	Upper Limit of Normal
WHO	World Health Organization
VPA	Valproic Acid

3 PROTOCOL SYNOPSIS AND RESEARCH SUMMARY

Please see separate upload in eIRB.

4 STUDY SCHEMA

5 BACKGROUND AND SIGNIFICANCE

5.1 Study Disease

Seizures are a debilitating complication of brain tumors. Aberrant and repetitive neuronal firing leads to the generation of seizures. Approximately 75% of patients with low grade tumors and 25% with high grade tumors suffer from seizures compared to 0.5-1% of the general population². Slower growing, low grade tumors are associated with higher epileptogenicity, while faster growing, high grade tumors are associated with seizures secondary to mass effect³. Higher seizure frequency has been associated with reduced cognitive function and Health-Related Quality of Life (HRQOL) and strips patients of driving privileges for 6 months on average in the US, thus affecting daily functional activities of living⁴. While surgery can be potentially curative of tumor-related seizures by resecting the nidus of seizure activity, it could also cause seizures due to irritation of the cortex, hemorrhage at the surgical site, and cerebral hypoxia and acidosis during surgery⁵.

The current guidelines recommend against peri-operative seizure prophylaxis in patients who have never had a seizure, and to taper Anti-Epileptic Drug (AED) therapy after the first post-procedure week^{6,7}. However, these guidelines were based on older generation AEDs [(Phenytoin (PHT), Phenobarbital (PBT), and Valproic Acid (VPA))] that were associated with significant side effects and drug-drug interactions. Since these guidelines were published in 2000, and reaffirmed in 2003 and 2008, newer generation AEDs have emerged with more favorable side effect profiles⁸. LCM, a third generation AED and LEV, a second generation AED, are both well tolerated with unique mechanisms of action.

Given the reduced risk of adverse event occurrence with newer AEDs, the clinical use of AEDs as prophylaxis has increased⁹; however, there have been no updated guidelines and there is a lack of clinical trial data to reflect this practice. LCM is US Food and Drug Administration (FDA) approved as adjunctive and monotherapy for partial-onset seizures and LEV is approved as adjunctive therapy^{10 11}. Their promising roles in brain tumor patients continue to be explored.

5.2 Study Agents

5.2.1 Mechanism of action

Lacosamide: LCM is a sodium channel blocker, enhancing slow inactivation, which is unique. Other sodium channel blocker AEDs enhance fast sodium channel inactivation¹². The activation state of voltage-gated sodium channels in the cells determines the potential for neuronal excitability¹². Sodium channels can either be in the resting, fast inactivated, or slow inactivated state (Figure 1A). In the resting state, the sodium channels are closed and can be opened by the depolarization of the membrane potential and therefore lead to neuronal activity¹³. Shortly after depolarization, the sodium channels shift into the fast inactivated state; they close their channels from inside the neuron and are unable to be activated¹³. Older generation AEDs work by prolonging this state (CBZ, PHT, and LTG)¹³. After the fast inactivated state, sodium channels return to their resting state¹³. However, in conditions of prolonged depolarization and repetitive neuronal stimulation, the sodium channels can assume a slow inactivated state by closing the pore inside the channel¹³. LCM works by enhancing this effect¹³. In doing so, LCM stabilizes hyperexcitable neuronal membranes that are most associated with seizures¹³. At the same time, it does not affect the ability to recover from slow inactivation; thus, it inhibits neuronal firing and reduces long-term sodium channel availability without affecting physiological function¹³. Chemically, it is a member of a series of functionalized amino acids¹³. Its chemical structure is $C_{13}H_{18}N_2O_3$ and its active drug substance is (R)-2-acetamido-N-benzyl-3-methoxypropionamide (Figure 1B)¹³.

[figure not shown]

Figure 1. A. Voltage-gated sodium channels and the role of LCM¹⁴.
B. Chemical structure of lacosamide (C₁₃H₁₈N₂O₃)¹⁴

Levetiracetam. LEV's anti-epileptic properties have been widely studied, but a single mechanism has yet to be elucidated. Its primary mechanism of action is binding to the synaptic vesicle protein SV2A, an essential

presynaptic membrane protein in neuronal transmission that is expressed ubiquitously in the brain¹⁵. By doing so, LEV decreases neurotransmitter release in states of epileptiform burst firing¹⁶.

LEV also inhibits calcium release from intraneuronal stores and high voltage activity (N-type) calcium channels¹¹. In regards to intraneuronal stores, LEV has been shown to inhibit the Inositol 1,4,5-triphosphate (IP3) and Ryanodine (RyR) receptors, two major receptors involved in calcium-induced calcium release (CICR), which effectively decreases intracellular calcium ($[Ca^{2+}]_i$)¹⁷. Ca^{2+} is part of important second messenger systems associated with neurotoxicity and neuronal plasticity¹⁷. Elevations in ($[Ca^{2+}]_i$) and alterations in calcium homeostatic mechanisms have been implicated in acquired epilepsy resulting from injury¹⁷. Thus, LEV's effect on calcium plays a part in its anti-epileptic ability.

LEV's impact on GABAergic (transmitting or secreting gamma-aminobutyric acid) mechanisms has been both favored and rejected, with discoveries only applicable or studied in specific diseases, such as those related to mesial temporal lobe epilepsy and not necessarily tumor related epilepsy^{18,19}.

Lastly, LEV has also been suggested to inhibit O-6 methylguanine-DNA methyltransferase (MGMT)²⁰. While not directly related to its anti-epileptic effect, it is relevant in this population, since MGMT is a Deoxyribonucleic Acid (DNA) repair protein that plays a role in resistance of gliomas to alkylating agents²⁰. Inhibiting MGMT thus inhibits malignant glioma cell proliferation, and increases sensitivity of gliomas to temozolomide, first-line chemotherapy for malignant gliomas²⁰.

LEV's chemical formula is $C_8H_{14}N_2O_2$ ¹⁵. It is the S-enantiomer of a-ethyl-2-oxo-1-pyrrolidine acetamide¹⁵.

5.2.2 Pharmacokinetics

Lacosamide. LCM's time to peak is 1-4 hours and the half-life is 13 hours, allowing for twice daily dosing²¹. LCM achieves steady-state concentrations after 3 days of BID dosing¹⁴. It has negligible protein binding¹⁴. Therapeutic drug monitoring is not routine given its predictable pharmacokinetics, except in instances of liver and/or kidney failure or to evaluate drug compliance²². Its absorption is not affected by food intake²³.

Levetiracetam. LEV's time to peak is 0.5-1 hour and the half-life is 6-8 hours^{15,24}. It achieves steady-state concentrations after 48 hours of BID dosing²⁵. LEV does not require routine drug monitoring for therapeutic levels because of its predictable pharmacokinetic profile and wide therapeutic margin^{11,15}. It has negligible protein binding²⁶. Its absorption is not affected by food intake¹⁵.

LCM and LEV are both renally cleared²⁷. Approximately 40% of LCM is excreted unchanged, 60% as an inactive metabolite formed by the liver (via several Cytochromes P450 (CYP450) and CYP-independent mechanisms, mainly cytochrome CYP2C19), and the remainder as a polar fraction thought to be serine derivatives^{10,28}. Nearly 100% of LEV is excreted by the kidneys, approximately 66% unchanged and the rest as a metabolite formed by hydrolysis in the blood^{29,30}.

5.2.3 Formula dosing

Lacosamide. LCM is available in IV, oral liquid and oral tablet formulations and has near 100% oral bioavailability²¹. It is dosed twice a day with a usual starting dose of 50mg BID for adjunctive therapy or 100mg BID as monotherapy^{10,21}. It can alternatively be initiated with a single loading dose of 200mg, followed by a maintenance dose regimen of 100mg BID approximately 12 hours later¹⁰. The maintenance dose can be titrated 50mg BID over a week to a maximum dose of 400mg/day^{21,31}. Discontinuation of LCM should be done gradually with a weekly taper of approximately 200mg a week¹⁰.

No dose adjustment of LCM is necessary in mild to moderately renally impaired patients; however, in patients who have creatinine clearance (CrCl) <30 ml/min and are diagnosed with end stage renal disease (ESRD), the maximum recommended dose is 300mg/day³². The maximum recommended dose for patients with mild to moderate hepatic impairment is 300mg/day, mainly attributed to associated renal dysfunction in patients with

moderate hepatic impairment¹⁰. LCM has not been systematically studied in patients with severe hepatic impairment, and is thus not recommended for these patients²³.

Levetiracetam. LEV is available in IV, oral liquid and oral tablet formulations, including extended release¹⁵. It has near 100% oral bioavailability. It does not require slow titration during initiation of therapy²⁵. LEV is usually dosed twice a day, unless it is the extended-release form, which is once a day. The usual starting dose is 500-1000mg BID, with a maximum dose up to 3000mg/day¹⁵. Discontinuation of LEV should be done gradually as prescribed by the primary physician.

LEV must be renally adjusted for patients with CrCl less than or equal to 80 ml/min/1.73m²³³. It does not need to be adjusted for mild-to-moderate liver impairment, but it does need to be reduced for severe liver impairment, mainly because often patients with severe liver dysfunction also have some renal impairment³⁴.

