Doses will be either LCM 100mg twice a day (BID) (Arm A), LEV 1000mg BID (Arm B), or no AED (Arm C). If a patient is randomized to Arm C and undergoes tumor mapping, the patient is allowed to receive one dose of AED in the operating room. If a patient is randomized to Arm A or Arm B and takes the morning dose of their AED, they do not need an intra-operative dose of AED. If a patient has a seizure during the post-procedure period, AEDs will be adjusted at the discretion of the treating physician. However, if a patient has intolerable side effects, patients will be changed to a different dose of the same medicine before consideration of another AED [i.e., BID to four times a day (QID) dosing if patient experiences diplopia on LCM].

Patients with high-grade tumors (newly-diagnosed or transformed) will be treated with standard radiation and temozolomide therapy per the Stupp protocol^{25,70}. For these patients, an AED taper will be initiated at the first clinic visit after completion of radiation. For patients with a low-grade tumor or recurrent disease of any grade, an AED taper will be initiated at the first scheduled post-procedure visit, approximately 6-10 weeks after the operation. LCM will be tapered by 100mg a week one week at a time. LEV will be tapered 500-1000mg one week at a time.

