7.1.2 AED titration

If a patient experiences seizure during the follow up period, AED doses will be modified per treating physician preferences.

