9 SUBJECT ELIGIBILITY

9.1.1 Inclusion Criteria

1. Patients with a suspected diagnosis of new, recurrent, or transformed glioma (WHO grade I-IV) or brain metastasis scheduled for MSR at DUMC;
2. Safe for surgery per treating neurosurgeon;
3. Due to the potential implications of the treatment on the developing CNS, all patients must be ≥ 18 years of age at the time of entry into the study;
4. Laboratory Studies:
 - a. Total bilirubin, Serum Glutamic Oxaloacetic Transaminase (SGOT), Serum Glutamic Pyruvic Transaminase (SGPT), Alkaline Phosphatase (ALK) ≤ 1.5 x upper limit of normal (ULN)
 - b. Creatinine ≤ 1.5
5. A signed informed consent form approved by the Duke University Institutional Review Board (IRB) will be required for patient enrollment into the study. Patients or their Legally Authorized Representative (LAR) must be able to read and understand the informed consent document and must sign the informed consent indicating that they are aware of the investigational nature of this study. Treating physicians at the time the protocol is presented are able to determine based on their clinical judgment whether patients lack the capacity and require a LAR to sign the consent form.
6. Patients of child bearing potential or with partners of child-bearing potential must agree to practice recommended contraceptive methods to prevent pregnancy during treatment and for 1 month after the last dose of AED for women and men.

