9.1.2 Exclusion Criteria

1. Pregnant or need to breast feed during the study period (Negative urine β -HCG test required), or unable to maintain use of contraception while on study and for 1 month after the last dose of AED;
2. Patients already on AED(s) specifically to treat seizures will be excluded. Those patients taking AEDs for any diagnosis other than seizures will be included (e.g. Gabapentin for neuropathic pain, Topiramate for migraine, benzodiazepines as sleeping aid, etc). Patients taking AEDs for seizure prophylaxis and without clear history of seizures will be included;
3. Known history of epilepsy/seizure disorder;
4. Known history of dependency/abuse of psychopharmaceuticals, alcohol, illicit drugs or narcotics;
5. Any significant medical or psychiatric illness that cannot be adequately controlled with appropriate therapy or would compromise the patient's ability to tolerate therapy, per the discretion of the treating investigator;
6. Known allergy to LCM or LEV.

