10.2 Study Period

Day 0 and prior (diagnosis): occurring at least within 48 hours prior to MSR

- Randomization
- Initiate AED, per Section [7.1.1](#) (LCM 100mg BID or LEV 1000mg BID)
- Characterize seizure type, if applicable, (i.e., simple partial, complex partial, or generalized)

Week 0-6

- Management of AEDs for any seizure events or adverse events will be left at the discretion of the treating physician. If side effects occur, adjusting dosing of current AED before changing AEDs is recommended.

Week 6-10: at the first planned post-procedure visit (LGG or brain metastasis) or first visit after radiation (HGG), the following study endpoint data will be collected only for the 30-day post-procedure time period

- Collection of calendar, if not already obtained from the REDcap database
- CMP and CBC with differential to assess resolution of toxicity
- AESI (please see Section [7.1.4](#))
- Number of readmissions, ED visits, provider communications during the 30-day post-procedure phase
- Number of dose adjustments, additions or discontinuations of AED(s) during the 30-day post-procedure phase
- Initiate weaning of the AED per discretion of the treating physician, for example:
 - LCM 100/50mg x1 week, 50/50mg x 1 week, 50mg daily x 1 week, then off
 - LEV 1000/500mg x1 week, 500/500mg x 1 week, 500mg daily x 1 week, then off

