 - Seek attention for personality change: It can take values “Yes” or “No”.
 - Feeling after treatment of personality change: It can take values “Better”, “Same”, or “Worse”.
2. Duration of initial admission stay for MSR: variable “duration_stay” will be used. It is a continuous variable.
 3. Intra-operative AED use: variable “aed_use” will be used. It can take “Yes” or “No”.
 - AED specification: variable “spef_aed” will be used. it can take values “Lacosamide (VIMPAT)” or “Levetiracetam (Keppra)”.
 4. Provider communications (email, telephone, or additional clinical visits) that occurred within 30 days of MSR. It includes:
 - Contacted provider: It can take values “Yes” or “No”.
 - number of contacts: it can take values 1-5.
 - Communication method: It can take values “E-mail”, “Phone”, “In-person (clinic visit)” or “Other”.
 5. Changes in dosages, type of AED, addition or discontinuation of AED that occur within 30 days of MSR
 - Discontinued AED: Did you discontinue your prescribed anti-epileptic drug (AED) since the last questionnaire? It can take values “Yes” or “No”.
 - Prescription modified: It can take values “Yes” or “No”.
 - Additional AED prescription: Have you been prescribed an AED in addition to your already prescribed AED since the last questionnaire? It can take values “Yes” or “No”.
 - Missed doses: Have you missed any doses since the last questionnaire? It can take values “Yes” or “No”.
 6. Patients experiencing post-procedure seizures during the 30-day postoperative phase.
 - Have you experienced a seizure since the last questionnaire? It can take values “Yes” or “No”.
 - Number of seizures: It can take values 1-5 and >5.

8. Exposures

Patients were randomized into 3 treatment groups: 1) Arm A - Lacosamide (Vimpat) 100mg twice a day; 2) Arm B - Levetiracetam (Keppra) 1000mg twice a day; 3) Arm C - or no anti-epileptic (anti-seizure) drug. Variable “treatment” will be used.

9. Demographics

Age at consent: variable “consent_age” will be used, It is a continuous variable.

Race: A categorical variable. It can take values: “White/Caucasian”, “Black/African-American”, “Asian” “Native American”, “Native Hawaiian or Other Pacific Islander”, “Other”, or “Unknown”.

ethnicity: A categorical variable. It can take values: “Hispanic or Latino”, “Not Hispanic or Latino”, “Unknown”, “Not Reported”.

Gender: A categorical variable. It can take values “Male” or “Female”.

Medical history

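### The protocol's own renal dosing rule for levetiracetam is not carried into the Arm B dosing sections, and the creatinine screen admits patients to whom it applies

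*Protocol*

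**What the plan says.** Section 5.2.3 of the protocol, which is background on dosing, says: "LEV must be renally adjusted for patients with CrCl less than or equal to 80 ml/min", indexed to 1.73 m². It does not say what the adjusted dose is. The same section says lacosamide (LCM) needs no change in mild to moderate renal impairment, so the point concerns Arm B only.

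The operative sections give one levetiracetam (LEV) dose. Section 7.1 fixes Arm B at 1000 mg twice daily. Section 10.2 repeats it for initiation: "LCM 100mg BID or LEV 1000mg BID". SAP section 8 has "Arm B - Levetiracetam (Keppra) 1000mg twice a day". None mentions renal function.

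The only renal eligibility limit, in section 9.1.1, is "Creatinine ≤ 1.5", without a unit. Creatinine clearance (CrCl) is not an inclusion or exclusion criterion, and Table 2 does not list its calculation.

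Three provisions allow discretion. Exclusion 5 (section 9.1.2) covers a significant illness that would compromise the patient's "ability to tolerate therapy, per the discretion of the treating investigator". Section 10.2 adds: "Management of AEDs for any seizure events or adverse events will be left at the discretion of the treating physician". Section 7.1.2 says that after a seizure "AED doses will be modified per treating physician preferences".

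**The concern.** A reader of section 5.2.3 would expect the dosing sections to say how an Arm B patient with CrCl of 80 or less is started. They do not. Staff who follow 7.1 and 10.2 as written give the flat dose to everyone. A prescriber who adjusts at initiation departs from the written Arm B dose, and the protocol does not say whether that is a deviation or a dose change to be counted under section 13.6.5.

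What is at stake is patient safety and internal consistency. Section 5.2.2 says nearly all LEV leaves through the kidneys, so the same dose gives higher exposure when clearance is low. Section 5.2.5 lists behavioural effects, somnolence and cognitive effects for LEV, and section 5.2.6 links raising its dose to more behavioural side effects.

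**Working it through.** The plan states no figure on this point, so there is none to reproduce. The check has two steps.

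**Step 1: does any other text supply a starting-dose rule?**

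- Section 7.1 allows a different dose for intolerable side effects. Sections 7.1.2 and 10.2 allow changes for seizures or adverse events. All are reactions to an event after the drug is started.
- Exclusion 5 decides who enters, not what dose an eligible patient receives.
- Section 7.2 says the doses rest on FDA-approved standard dosing. Section 8.2 says the package inserts are uploaded. Neither tells anyone to dose Arm B by renal function.

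No rule is found.

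**Step 2: does the creatinine limit already screen out patients with CrCl of 80 or less?**

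Inputs from the documents: creatinine limit 1.5 (section 9.1.1) and CrCl limit 80 (section 5.2.3). Assumptions not in the documents: creatinine in mg/dL, the Cockcroft-Gault formula, and the ages, weights and heights used.

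Formula: CrCl = (140 − age) × weight / (72 × creatinine), times 0.85 for women.

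Age 60, 70 kg:

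- Creatinine 1.5: man 5600/108 = 51.9; woman 51.9 × 0.85 = 44.1.
- Creatinine 1.0: man 5600/72 = 77.8; woman 66.1.
- Creatinine at which CrCl is exactly 80: man 5600/(72 × 80) = 0.97; woman 0.97 × 0.85 = 0.83.

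The section 5.2.3 limit is indexed to body surface area. With assumed heights of 175 cm (man) and 163 cm (woman), the Mosteller areas are 1.845 and 1.780 m². Multiplying by 1.73/area gives 48.6 and 42.8 at creatinine 1.5. Indexing does not change the conclusion for this patient.

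Varying age at 70 kg (unindexed, ml/min):

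| Creatinine | Sex | Age 30 | 45 | 55 | 65 | 75 |
|---|---|---|---|---|---|---|
| 1.5 | Man | 71 | 62 | 55 | 49 | 42 |
| 1.5 | Woman | 61 | 52 | 47 | 41 | 36 |
| 1.0 | Man | 107 | 92 | 83 | 73 | 63 |
| 1.0 | Woman | 91 | 79 | 70 | 62 | 54 |

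Varying weight (unindexed): at creatinine 1.5, CrCl exceeds 80 below age 140 − 8640/weight for a man, where 8640 = 80 × 72 × 1.5. That is age 32 at 80 kg and about 54 at 100 kg. For a woman of 100 kg it is 140 − 8640/85, or about 38. At creatinine 1.0, a 60-year-old man of 90 kg has CrCl 80 × 90/72 = 100, or about 83 indexed at 175 cm, and needs no adjustment.

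So the limit of 1.5 admits patients at or below 80. How far below 1.5 the issue reaches depends on age, sex and weight.

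**The case against.** The strongest reply is that section 5.2.3 is background that summarises cited pharmacology, not a trial instruction. Both drugs are prescribed through ordinary pharmacies (section 8.4), the package inserts are on file, and nothing forbids usual renal dosing. The flat dose lies within the usual starting range in section 5.2.3, and section 5.2.2 describes the therapeutic margin of LEV as wide. Many of the relevant side effects are collected as adverse events of special interest, dosing can be changed when they occur, and the investigator may withdraw a patient for safety. All of this stands, and it limits the weight of the point. It does not supply the missing starting-dose rule.

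A reader might infer that 1000 mg twice daily is an overdose for anyone at or below 80. The documents do not support that. They require adjustment but give no adjusted dose. In the same section, renal adjustment of LCM is expressed as a lower maximum, not a lower starting dose. If the LEV adjustment took that form, 2000 mg/day might comply at some clearances, since it is already below the 3000 mg/day maximum.

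A reader might also convert clearance into an equivalent daily dose and compare it with that maximum. Such a calculation needs an exposure model that the documents do not provide, so none is offered here.

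**Conclusion.** The point holds as a gap between sections. The protocol states a mandatory renal rule for LEV, the three places that set the Arm B dose omit it, and the renal screen does not make it unnecessary. That eligible patients fall below 80 rests on the assumptions of mg/dL and Cockcroft-Gault: about 52 ml/min for a man and 44 for a woman aged 60 and 70 kg at the limit. The number affected is unknown, because the documents give no distribution of creatinine, age or weight.

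It would be wrong to infer a threat to the main result. The primary endpoint, the 232 patients and the power do not depend on this. Any effect on the LCM versus LEV adverse event comparison in section 13.5 is not quantified in the documents, and none is claimed. This is a cheap improvement on patient-safety grounds.

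**What to change.** - **Section 9.1.1:** state the creatinine unit.
- **Section 10.1:** calculate CrCl from the screening metabolic panel (CMP) with a named formula, on the same scale as the section 5.2.3 limit. Record weight, and height if the value is indexed.
- **Sections 7.1 and 10.2:** add that Arm B patients with CrCl of 80 or less start at a dose consistent with the renal dosing in the package insert on file. Say that this is protocol-specified dosing, neither a deviation nor a dose change under section 13.6.5.
- **SAP section 8:** carry the same wording.

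Parts of the SAP are in the past tense. If enrolment is already complete, an amendment cannot change starting doses; report the actual Arm B starting doses by baseline CrCl instead.

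The cost is a few lines of text and one calculation from blood already drawn. Weight and height are not listed as separate items in Table 2 and would have to be recorded. No extra visit, test or patient is needed. The downside is a slightly less uniform Arm B dose.
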